1. INTRODUCTION

Non-Hodgkin's lymphoma (NHL) comprises a heterogeneous group of lymphoproliferative diseases, resulting from a malignant transformation of mature B cells. Follicular Lymphoma (FL) is the second most frequent NHL in the US and Western Countries, accounting for about 10- 20% of all newly diagnosed NHLs and 70% of all indolent Lymphomas.^{1, 2} The incidence of FL, as of other non-Hodgkin lymphoma, is rising, but varies between geographical regions and racial groups, being higher in developed countries and lower in Asian and sub-Saharan African countries.³ In the US the frequency is about one case for every 20.000 or 250000 people per year, whereas in Italy the incidence is approximately 11% and the standardized annual incidence rate is 2 per 100000 people.^{3,4} Generally, the incidence increases with the age and the disease is typically diagnosed during the 5th to 7th decade. Nearly 10% of patients are diagnosed as young adults (age 18-40). Moreover FL is slightly more prevalent in the female population with a male to female ration of 1:1,7.²⁻⁵

The pathogenesis of FL is best explained by a model that takes into account genetic alterations harbored by the neoplastic B cells and an immunological hypothesis that suggests prominent crosstalk between the tumor cells and non-neoplastic immune cells in the tumor microenvironment, which include T cells, macrophages, follicular dendritic cells and stromal elements.⁶ It is well known that the translocation t(14;18), present in about 80-90% of FL, is assumed to represent the first oncogenic hit of lymphomagenesis. This somatic rearrangement juxtaposes the B cell Lymphoma 2 (BCL2 gene) (located on chromosome 18) under the influence of transcriptional enhancers of immunoglobulin variable heavy chains (IgH), thus leading to constitutive BCL2 protein expression; the cells then slowly proliferate, but do not die by apoptosis, and hence proliferate uncontrolled and acquire genetic alterations.^{7,8} The presence of the t(14;18) translocation alone is most likely insufficient for complete neoplastic transformation. Other rearrangements and mutations provide the malignant cells with a growth advantage.⁹

The diagnosis is based on examination of excisional biopsy samples, including immunohistochemistry. According to the 2016 WHO classification of Tumours of Haematopoietic and Lymphoid Tissues, currently 4 variants of FL are recognized: in situ FL, duodenal-type FL, testicular FL and the diffuse variant of FL.² FL is graded by counting or estimating the absolute number of centroblasts in 10 neoplastic follicles per high power microscopic field (**Appendix A – Grading of Follicular Lymphoma**).¹⁰

The clinical course of FL is typically indolent, with impressive responses to initial treatment. Nevertheless, frequent relapses occur, that need additional therapeutic interventions resulting in shorter remission duration and increased risk of drug resistance, and most of the patients will eventually die of their disease. As a consequence, currently the median progression free survival

(PFS) is between 6-7 years and the overall survival (OS) ranges from 10 to 15 years. Despite the observed improvement in survival over time, the outcome is not favorable for all patients affected by the disease, and FL is therefore considered incurable. Indeed, some patients, about 20% of newly diagnosed FL, will undergo early progression after treatment (<24 months) or will present with chemoresistance disease.^{11, 12} In addition, from 20 to 40% of patients will experience transformation into aggressive lymphoma, mostly diffuse large B cell lymphoma.¹³

Multiple parameters were shown to have prognostic significance, either related to the patient (age, sex, vitamin D), the lymphoma (stage, bone marrow involvement, LDH, β 2M, and early progression of disease), or to the effect of the disease on the patient (B symptoms, performance status); several scoring systems have been proposed to enable more accurate prognostication (FLIPI, FLIPI-2, PRIMA-PI) (*Appendix B – Prognostic scores*).^{14–19} Techniques such as GEP have increased our understanding of the biology of FL, and novel prognostic scores like the m7-FLIPI now incorporate biologic markers such as mutational status of specific genes.²⁰

However, current knowledge is insufficient to guide treatment decisions in patients with high risk disease. Especially for patients who relapse early after immuno-chemotherapy, the optimal therapeutic strategy is not known.

Due to the indolent nature of the lymphoma, most patients are diagnosed with advanced disease, including bone marrow involvement, in the absence of B symptoms.² The disease is staged according to the criteria of the Lugano classification (*Appendix C – Lugano modification*).²¹ Currently, the treatment of patients is still guided by staging. Radiotherapy with curative intent is proposed for patients with stage I or II disease. For patients with contraindications for radiotherapy, clinical observation or treatment with rituximab, alone or in combination with chemotherapy, may be considered.^{22, 23} For patients with advanced disease, no curative therapy is established, and treatment should only be initiated in case of symptomatic disease according to the GELF criteria (*Appendix D – GELF criteria*).

The choice of treatment in patients with advanced disease varies according to patient's performance status, age, comorbidities and purpose of therapy, but usually comprises of rituximab in combination with chemotherapy such as CHOP, CVP, FM, bendamustine, or novel agents such as lenalidomide for patients enrolled in clinical trials.^{24–26}

Response evaluation should be performed midterm and after completion of chemotherapy. Patients who achieve a complete or partial remission can be treated with rituximab maintenance for 2 years as this results in an improvement of PFS (59% versus 43% after 6 years, $p < 0.0001$).²⁷ On the other hand, patients with an inadequate response should be evaluated for early salvage regimens. The use

of FDG_PET-CT after completion of chemotherapy induction has been recommended for prognostic reasons since persistent PET positivity identifies a worse prognosis group.²⁸

FL follows a chronic relapsing course and a new course of treatment is indicated based on GELF criteria. Histologic documentation of progressive disease and exclusion of transformation² are highly recommended before the start of new lines of therapy.² For patients requiring a second line of treatment, the chemotherapy regimen used in first line may be employed again if relapse occurs after an interval of at least 24 months. Otherwise, a non-cross-resistant scheme should be preferred. Obinutuzumab is an option for patients with rituximab refractory disease^{22, 23, 29} as well as the PI3K inhibitor idelalisib.³⁰ Autologous transplantation is an option to be considered as consolidation in first relapse, especially in young patients with short remission.³¹

The optimal treatment strategy in patients with early progressive disease is not well known. In recent years, novel insights into the biology of FL, and especially the role of the microenvironment, have resulted in the development of multiple novel treatment modalities. These new agents may ultimately improve the outlook for patients with FL with an unfavorable course, but for the development of the optimal therapeutic strategy, knowledge on the clinical and biological determinants of early refractory FL is needed.

2. OBJECTIVES

The purpose of the present study is (1) to define the prognosis of refractory/relapsed FL after second line therapy; (2) to report current treatment strategies; (3) to provide rationale for the design of novel treatments strategies.

3. ENDPOINTS

Primary Endpoints

- Rate of Progression of disease within 24 months from start of second line treatment (second POD24)

Secondary Endpoints

- Overall Survival (OS)
- Progression-free survival after second line therapy (second PFS)
- Complete response rate at 30 months (CR30) from start of second line treatment (second CR30)

4. STUDY DESIGN

This is an international, prospective, longitudinal, observational study of patients with histological diagnosis of follicular lymphoma refractory/relapsed after first line therapy.

4.1 Subject selection

Inclusion criteria

- Patients with initial diagnosis of follicular lymphoma, refractory/relapsed/transformed after first line therapy;
- All stages at the time of relapse;
- Histological grade 1-3a at the time of initial diagnosis;
- Age over 18 years;
- Availability of clinical data, including baseline information, comorbidities, data on disease localization, laboratory parameters at staging, features of treatment adopted and assurance of follow-up updating as requested - Data collection list (*Appendix E_Data collection list*)
- Diagnostic material available for review;
- Written informed consent.

Exclusion Criteria

- Age < 18 years

5. STUDY PROCEDURES

5.1 Patient enrollment and registration

Patients with histologically confirmed follicular lymphoma are registered in the study at the time of the first event after first line treatment. An event is defined as refractory/relapsed disease documented by biopsy, imaging, or clinical evaluation. Registration is based on the locally established histological diagnosis, with exclusion of cases diagnosed on fine needle aspiration cytology, while tru-cut core-needle biopsies are permitted in the study. Registration will be done on-line on a key restricted accessible web-database: the Investigator must complete the on-line registration form after obtaining informed consent dated and signed by the patient.

Investigators are requested to register consecutive cases diagnosed at each participating Institution (all patients satisfying Inclusion criteria without any further selection). Inclusion criteria will be checked at the Trial Office. A patient number (Patient ID) will be assigned strictly sequentially in ascending order as patient's eligibility is verified. In case a patient's eligibility is not confirmed by the Trial office and the patient is withdrawn from the study, the patient number will not be reused.

The assigned number will be used as the identification code for the subject. A space will be provided for the Clinician to enter a local alphanumeric code to better identify the patient.

5.2 Pathology review

Every registered case has to undergo histopathology review by a panel of experts. The reference pathologist will collect and review the pathology material sent by the participating centers, without knowledge of the clinical outcome of the patient. Both material obtained at diagnosis, and at relapse will be reviewed. Classification will be performed according to the World Health Organization recently published.²

5.3 Data collection list

The list of data that will be collected is shown in *Appendix E_Data collection list*.

5.4 Data collection modalities

Registration of patients and data collection will be performed on-line in an Electronic Case Report Forms (eCRFs). eCRFs must be reviewed and verified for accuracy by the local Investigator. Patients registered into the study will not be identified by name on any study documents to be collected, but will be identified by a Subject Identification Number (Patient ID).

The adoption of SSL03 technology will assure protection of subject's clinical data in web communications. Data access and management will be regulated by the use of passwords with different levels of admittance, providing that subject confidentiality be respected. Once the patient has been registered, an email is sent to the local Investigator, the local Data Manager and to the Trial Office. Data will be stored into different electronic forms. After completion of a single form, data will be locked and it will not be possible to modify, unless a specific and documented written query is submitted to the Trial Office. To guarantee the data quality, the eCRF must be completed in real time.

6. STATISTICAL CONSIDERATIONS

6.1 Sample size

Sample size calculation is based on the aim of defining the prognosis of refractory/relapsed FL after second line therapy. To evaluate number of recordable events, we hypothesize that PFS after refractory/relapse has a risk function which follows Weibull distribution with time parameter (in months) $\lambda = 0.008$ and form parameter $p = 0.97$. After 10,000 Monte Carlo simulations we calculated that with **500** prospective cases enrolled, we would observe **145** events at the end of the study. If, for

epidemiological reasons, it will be difficult to record 500 cases, we plan to enroll all cases in two years from the study start.

6.2 Statistical analysis plan (SAP)

Descriptive variables: continuous variables will be expressed as median and inter-quartile distance, while categorical variables will be reported as absolute frequencies and percentages. Continuous variables will be compared with the use of the Mann-Whitney test (2 groups) or the Kruskal-Wallis test (three or more groups), while categorical variables will be compared through the use of Fisher's exact test or Chi-square test as appropriate.

Survival analyses: survival functions will be calculated utilizing Kaplan-Meier method and survival rate at specific time-points will be expressed with the correspondent 95% confidence interval (95CI). The effect related to potential variables with prognostic value will be estimated through Cox proportional risk regression and will be expressed as hazard ratio (HR) with 95CI. Risk proportionality will be verified through Schoenfeld partial residual analysis, both graphically and through cubic-spline smooth linear regression. The influence of residues will be evaluated through likelihood displacement as a function of the residues martingala analysis.

6.3 Study duration

Patients will be followed for at least two years after enrollment. However, a five year follow-up period is desirable (an update is requested at least every 6 months).

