6.4 Endpoint definition

The endpoints of interest in the present study have been adapted from the Standardize Response Criteria for Non-Hodgkin's Lymphoma and from Recommendations for Revised Response Criteria for Malignant Lymphoma (*Appendix C2_Revised Response Criteria for malignant lymphoma*). In particular:

- Second POD24 is defined as the rate of progression of disease at 24 months after the second line treatment;
- OS is measured from the date of diagnosis until death from any cause;
- Second PFS is measured from the date of study entry until the date of disease progression or death from any cause;
- Second CR30 is defined as the rate of complete remissions at 30 months from start of second line treatment.

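### The binding two-year follow-up from enrolment is at least 6 months too short for second CR30 and leaves no margin for second POD24

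*Protocol*

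**What the plan says.** Section 6.3 of the protocol sets the only binding follow-up: "Patients will be followed for at least two years after enrollment". It continues: "However, a five year follow-up period is desirable (an update is requested at least every 6 months". The longer period is a wish, not a requirement.

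The enrolment clock starts at relapse or refractoriness, not at treatment. Under section 5.1 patients are "registered in the study at the time of the first event after first line treatment".

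The two fixed-time endpoints run from a different origin. Section 3 gives the primary endpoint as "Rate of Progression of disease within 24 months from start of second line treatment (second POD24". Section 6.4 states: "Second CR30 is defined as the rate of complete remissions at 30 months from start of second line treatment".

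Section 6.4 also words the primary endpoint differently from section 3: "Second POD24 is defined as the rate of progression of disease at 24 months after the second line treatment". This does not say whether the count begins at the start or the end of treatment.

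On the gap between relapse and retreatment, the Introduction says only: "FL follows a chronic relapsing course and a new course of treatment is indicated based on GELF criteria". The protocol neither states nor limits the time from registration to second-line treatment.

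**The concern.** A fixed-time endpoint can be reported only for patients whose status at that time is known. The protocol guarantees 24 months counted from one date, but asks for status at 30 months, and for progression up to 24 months, counted from a date that is the same or later. A site that meets section 6.3 exactly would stop collecting data before month 30 for every patient treated at or after registration.

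For second CR30 the loss is lopsided. A patient who dies before month 30 is known not to be in remission then, while a patient in remission when follow-up stops cannot be confirmed. A simple rate that counts the known failures and leaves out the unconfirmed patients would be too low.

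For second POD24, patients who start treatment after registration could leave observation before the 24-month window closes. Because updates are requested every 6 months, the last recorded status may also fall before month 24 even when treatment starts on the day of registration.

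**Working it through.** **Inputs.** Minimum follow-up: 24 months from enrolment (6.3). Update interval: 6 months (6.3). CR30: 30 months from second-line start (3, 6.4). POD24: 24 months from second-line start (3). PFS: Weibull with λ = 0.008 and p = 0.97; 500 cases; 145 events (6.1). Lag d from registration to second-line start: not given, so taken as 0, 3, 6 and 12 months. Accrual: two years appears in 6.1, but only as a fallback if 500 cases are hard to reach; otherwise not stated.

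**Step 1: the plan's own event count.** Let accrual be uniform over a months, with closure f months after the last enrolment. Expected events = 500 × the average of 1 − S(t) for t between f and f + a. The Weibull form is not stated, so both are used: A, S(t) = exp(−λt^p); B, S(t) = exp(−(λt)^p). With a = 24 and f = 24 this gives 113 (A) or 129 (B), not 145. Several longer schedules come within 3% of 145 (table). The schedule behind the stated figure therefore cannot be identified, and no single schedule can be treated as the plan's.

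**Step 2: the guaranteed minimum.** Observation guaranteed from second-line start = 24 − d.

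- CR30 shortfall = 30 − (24 − d) = 6 + d, that is 6, 9, 12 and 18 months at d = 0, 3, 6 and 12.
- POD24 shortfall = 24 − (24 − d) = d, that is 0, 3, 6 and 12 months.

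This step needs no accrual assumption. To cover CR30 for every patient, a minimum counted from enrolment would have to be 30 + d: 30, 33, 36 or 42 months.

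**Step 3: illustrative shares under a common closure date.** Potential follow-up from enrolment is then uniform between f and f + a. The share ending before month m from treatment start is (m + d − f)/a, held between 0 and 1. For example, with 24 + 24 and d = 3, CR30 gives (30 + 3 − 24)/24 = 37.5%.

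| Accrual + closure (months) | Expected events A / B | Ends before month 30, d = 0 / 3 / 6 | Ends before month 24, d = 0 / 3 / 6 |
|---|---|---|---|
| 24 + 24 | 113.4 / 128.6 | 25% / 37.5% / 50% | 0% / 12.5% / 25% |
| 36 + 24 | 128.7 / 145.3 | 16.7% / 25% / 33.3% | 0% / 8.3% / 16.7% |
| 48 + 24 | 143.0 / 161.0 | 12.5% / 18.8% / 25% | 0% / 6.3% / 12.5% |
| 24 + 30 | 129.3 / 146.1 | 0% / 12.5% / 25% | 0% / 0% / 0% |
| 24 + 36 | 144.3 / 162.7 | 0% / 0% / 0% | 0% / 0% / 0% |

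Of 500 patients, 25%, 37.5% and 50% are 125, 188 and 250. These are shares of potential follow-up. Patients with an earlier event are already observed for POD24, so fewer than these shares have an unknown outcome.

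**The case against.** The strongest reply is that section 6.3 sets a floor, not a stopping rule. Five years from enrolment would cover CR30 for any lag up to 60 − 30 = 30 months, and many centres may provide it. That stands as a limit on the likely loss. It does not secure the endpoint, because an optional extension can vary by centre and by date of enrolment. A separate analysis plan could not supply data that the protocol does not require sites to collect.

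A second reply is that section 6.2 specifies Kaplan-Meier estimates with confidence intervals at set time points, which accommodate patients censored before month 24. This largely stands for POD24, although 6.2 does not name that endpoint. In the 24 + 24 schedule with a 3-month lag, 87.5% of patients have potential follow-up to month 24 and the rest are censored between months 21 and 24. A reader might infer that the primary endpoint cannot be estimated. The documents do not support that, unless most patients stop at the minimum. The reply does not rescue CR30, which is a remission status at one time point.

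Third, the lags have no source in the protocol. The retreatment sentence is background in the Introduction, and the cohort includes refractory and transformed cases, so one lag for all is a simplification. The 24 + 24 schedule is also the least favourable row in the table and does not give 145 events. Both criticisms stand, which is why a range is shown.

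Fourth, a reader might infer that the missing outcomes are informative because late-treated patients are the ones lost. With a constant lag, loss depends only on the enrolment date, which is ordinary administrative censoring. Selection through late treatment is plausible, but nothing in the protocol shows it.

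**Conclusion.** The mismatch is certain for second CR30. The binding follow-up falls short by 6 months plus the lag for every patient treated at or after registration, and no other section closes the gap. A patient followed only for the minimum cannot be confirmed in remission at month 30.

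For second POD24 the minimum has no margin at zero lag and is short by the lag otherwise. This is mainly lost precision. If section 6.4 is read as counting from the end of second-line treatment, the shortfall grows by the length of that treatment.

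The share of patients affected is illustrative: 0% to 50% for month 30 across the schedules and lags tried, assuming uniform accrual, a common closure date and a constant lag. A reader might infer that CR30 would be available for nobody. That is the limiting case in which every centre stops at the floor, and the requested five years argues against treating it as the expectation. Nor does the failure of 24 + 24 months to give 145 events show that the figure is wrong, since longer schedules give it.

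This should be fixed. It is not graded higher because the certain defect concerns a secondary endpoint of an observational study.

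**What to change.** - In section 6.3, count the minimum follow-up of treated patients from the start of second-line treatment and set it at 36 months (30 months plus one 6-monthly update). Place the final data cut when the last treated patient reaches it.
- Keep at least two years from enrolment for registered patients who never start second-line treatment. They would otherwise have no defined minimum, although second PFS runs from study entry.
- Allow POD24 to be reported earlier, once all treated patients have 24 months from treatment start.
- In section 6.4, align the POD24 origin with section 3 (start of second-line treatment).

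The cost is a later final report and more of the existing updates. Relative to the present floor, at zero lag, this is 6 months to reach month 30 and up to 6 more for the update, so 6 to 12 months; any lag adds to it. The new minimum stays within the five years already called desirable for lags up to 60 − 36 = 24 months. No procedure or treatment changes.

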6.4 Endpoint definition

The endpoints of interest in the present study have been adapted from the Standardize Response Criteria for Non-Hodgkin's Lymphoma and from Recommendations for Revised Response Criteria for Malignant Lymphoma (*Appendix C2_Revised Response Criteria for malignant lymphoma*). In particular:

- Second POD24 is defined as the rate of progression of disease at 24 months after the second line treatment;
- OS is measured from the date of diagnosis until death from any cause;
- Second PFS is measured from the date of study entry until the date of disease progression or death from any cause;
- Second CR30 is defined as the rate of complete remissions at 30 months from start of second line treatment.

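### OS is timed from diagnosis in a cohort that is registered only at first-line failure, so it does not measure post-relapse prognosis and inflates hazard ratios for covariates tied to time to relapse

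*Protocol*

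**What the plan says.** Section 6.4 of the protocol defines the secondary endpoint: "OS is measured from the date of diagnosis until death from any cause". In the same list, "Second PFS is measured from the date of study entry until the date of disease progression or death from any cause".

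Section 4.1 admits "Patients with initial diagnosis of follicular lymphoma, refractory/relapsed/transformed after first line therapy". Section 5.1 says that they are "registered in the study at the time of the first event after first line treatment".

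The first purpose in section 2 is "to define the prognosis of refractory/relapsed FL after second line therapy". For the analysis, section 6.2 says that "survival functions will be calculated utilizing Kaplan-Meier method" and that prognostic effects will be estimated by Cox regression. It does not mention delayed entry.

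**The concern.** To be registered, a patient must have lived from diagnosis to first-line failure. A death in that interval cannot enter the data. If the OS clock starts at diagnosis and patients are treated as at risk from that date, the interval adds follow-up time in which no event was possible. This is left truncation, often called immortal time.

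Two results would suffer. First, the OS curve would not describe what happens after relapse, which is the question the study asks. Second, patients who relapse late contribute long event-free stretches only because they were enrolled late. Any covariate associated with the interval then looks prognostic. Early progression is such a covariate, and it is the clinical problem that motivates the study in the Introduction. Section 2 also intends the results to supply a rationale for new treatment strategies.

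**Working it through.** **1. Which diagnosis is meant.** Section 4.1 speaks of the initial diagnosis. Section 5.2 separates the two time points: "Both material obtained at diagnosis, and at relapse will be reviewed". Appendix E lists the date of histologic diagnosis apart from the date of progression or relapse. The natural reading of section 6.4 is therefore the original diagnosis of follicular lymphoma. Second PFS starts at study entry, so the two survival endpoints have different origins.

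**2. The plan's own figures.** The protocol states no OS figure. Its one computed figure, 145 events in 500 patients, concerns PFS. It reproduces as 500 × [1 − exp(−0.008 × 48^0.97)] = 144.8 if all patients are observed for 48 months. It has no bearing on the OS origin.

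**3. Level of the OS curve.** The inputs below are assumptions, because the documents give neither the interval among enrolled patients nor post-relapse mortality. The Introduction's median PFS of 6-7 years refers to the disease in general and serves only to set the upper end.

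- Post-relapse survival is exponential with 70% alive at 5 years: b = −ln(0.70)/5 = 0.0713 per year.
- Diagnosis-to-relapse time is exponential with median m: a = ln 2/m.
- Probability of being alive 5 years after diagnosis, for patients who relapse: (a·e^(−5b) − b·e^(−5a))/(a − b).

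| m (years) | a | e^(−5a) | 5-year OS from diagnosis | 5-year OS from relapse |
|---|---|---|---|---|
| 1 | 0.6931 | 0.0313 | 0.777 | 0.70 |
| 2 | 0.3466 | 0.1768 | 0.836 | 0.70 |
| 3.5 | 0.1980 | 0.3715 | 0.885 | 0.70 |
| 6.5 | 0.1066 | 0.5867 | 0.929 | 0.70 |

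For m = 2: (0.3466 × 0.70 − 0.0713 × 0.1768)/(0.3466 − 0.0713) = 0.836.

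**4. Hazard ratio for a covariate linked to the interval.** Let the covariate be relapse within 2 years of diagnosis. In the first 2 years on the diagnosis clock, every recorded death must fall in the early-relapse group, because the others have not yet relapsed and could not have been enrolled dead. The estimate is pushed upwards whatever the truth. Simulation under the assumptions of step 3, with 20,000 patients, follow-up of 2-4 years after relapse and no true effect, gives:

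| Median interval (years) | Cox HR, timed from diagnosis |
|---|---|
| 1 | 2.8 |
| 2 | 4.1 |
| 3.5 | 6.7 |
| 6.5 | 10.7 |

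The same data timed from relapse give 0.95-1.00, and timed from diagnosis with delayed entry 0.88-1.06. Repeat runs scatter. One with 6,000 patients gave 2.4, 4.2, 7.2 and 13.8 from diagnosis. About 2.5 to 12 is a fair summary, and the upper end is the least certain.

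**5. At the planned size.** A second simulation used 500 patients, median intervals of 12, 24 or 48 months (plus 3), 65% or 80% 5-year survival in the reference group, and censoring 24-48 months after entry. Across the scenarios completed, a true HR of 1 for early relapse became 2.7-6.6 from diagnosis (0.89-1.06 from relapse). A true HR of 2 became 5.0-12.9 (1.91-2.10 from relapse).

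**6. Hazard ratio for a covariate unrelated to the interval.** In the 500-patient simulation with a true HR of 2, the estimates are 1.81-2.00 from diagnosis and 1.84-2.09 from relapse. The difference is small.

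**The case against.** Several points on the other side are fair.

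- **The 5-year figure is a valid probability for its own question.** For patients who relapse, the chance of being alive 5 years after diagnosis really is higher than 5 years after relapse, because the clock starts earlier. Section 6.4 does not call it post-relapse survival. This stands. The fault is that the origin does not serve the aim in section 2 and that a reader will take the curve as prognosis of relapsed disease.
- **Not every hazard ratio is distorted.** A reader might infer that all OS hazard ratios are badly biased. Step 6 does not support that; the problem is confined to covariates associated with the interval.
- **No covariate is named.** Section 6.2 speaks only of variables of potential prognostic value. That early progression will be modelled against OS is an inference from the Introduction and from the data list in Appendix E. It is a likely use, but not one that the protocol fixes.
- **The size is not a property of this protocol.** A single hazard ratio of about 7 could be quoted for one assumed interval. The documents do not support any one value, so only a range is given.
- **OS is secondary.** A reader might infer that the study's main result is compromised. It is not: second POD24, second PFS and second CR30 do not start at diagnosis, and the sample size rests on PFS.
- **Delayed entry is only a partial remedy.** Patients who never relapse never enter the risk set, so a delayed-entry curve from diagnosis does not estimate OS of all patients with follicular lymphoma. It also assumes that the hazard at a given time since diagnosis does not depend on when relapse occurred.

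None of this removes the core. The origin precedes cohort entry, and the planned analysis takes no account of it.

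**Conclusion.** The point holds in limited form. As written, OS starts before any patient can be in the cohort, and ordinary Kaplan-Meier and Cox analysis treats the gap as time at risk. The resulting curve does not answer the study's question and looks more favourable than survival from relapse: about 78-93% against 70% at 5 years. A null hazard ratio for relapse within 2 years becomes about 2.5-12, against about 0.9-1.1 when timed from relapse. These sizes rest on assumed exponential times, 70% 5-year survival after relapse, 2-4 years of follow-up and median intervals of 1 to 6.5 years. The direction does not depend on the particular values. The time origin is stated in the protocol itself, so this is not a detail left to a separate analysis plan. Because OS is secondary and can be re-timed from collected dates, the grade is should-fix.

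**What to change.** In section 6.4, define OS from the date of study entry (registration at first relapse or progression) to death from any cause, for all registered patients. This is the origin that second PFS already uses. It also keeps registered patients who never start second-line treatment, whom an origin at treatment start would drop.

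If OS from diagnosis is also reported, label it as descriptive of patients who relapsed, analyse it with delayed entry at registration, and do not use it for prognostic hazard ratios.

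The cost is one sentence, plus one more if the descriptive analysis is kept. Appendix E already collects the dates of diagnosis, treatment start, progression or relapse, last contact and death, so no new data are needed and the sample size does not change.
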